#### **Risk-Benefit Ratio:**

Subjects participating the study will receive a monetary compensation to compensate for their time and effort. The results of this study can provide more knowledge about the role of intranasal oxytocin in autism and about the neural correlates of its action. It will also provide knowledge about the heterogeneity in oxytocin effects that could be related to different intrinsic factors (such as DNA methylation, clinical classification, genetic polymorphisms, environmental factors, metabolites and immune factors). It will also provide more information on the biological basis of social functioning in ASD. It is hoped that such knowledge will ultimately lead to a better

understanding of psychiatric disorders involving social behavioral deficits. These potential benefits outweigh the minimal risk this research poses to subjects.

## Type of information collected

- 1- We are collecting behavioral data from questionnaires and computerized social games and tasks. Responses to questionnaires, accuracy during games or tasks, reaction time will be collected and responses.
- 2- Video-taping participants and getting a photo during the clinical interview BB-CGI (see above).
- 3- Clinical diagnosis of severity of symptoms based on the BB-CGI that will rated by a psychiatrist.
- 4- Based on the video-taping, staff members will code behavioral and emotional expressions and verbal aptitudes of participants and synchrony with the experimenter.
- 5- Physiological measures from the sensor watch that will consist of temperature, electrodermal activity (or skin conductance), heart rate variability.
- 6- MRI scans of anatomy that will be kept for future
- 7- fMRI data (functional BOLD signal) in response to cues and in response to rest
- 8- Vital signs (BP, Temp, RR, HR), weight, height
- 9- General information form: the questions regarding participants are: medication, difficulties, current occupation, activities, social network, participation in behavioral therapy or group activities to stimulating social aptitudes, specific interest and knowledge, specific talents). The questions regarding subject's family will consist of: number of siblings, gender of siblings, education/occupation/social aptitudes of siblings, parents and grandparents, health-related questions, presence of any psychiatric, autism-related disorders.
- 10- Eye tracking data: eye movements of subjects while they are laying down in the scanner performing a task. We will quantify subjects' visual duration and fixation on regions of interest of the stimuli that are presented on the screen.
- 11- Physical that is performed by the NP.

## Specimens

3 Saliva samples will be collected for DNA analysis. We will use the Oragen DNA kits. Some samples might be used to quantify DNA methylation of OXTR and OXT gene or OXTR polymorphisms, MET gene. The remaining samples will be kept safe for potential future use. We will not collect saliva samples from healthy subjects.

8 blood samples (EDTA purple tubes of 10 ml each) will be collected per subject for all 4 MRI visits (4 blood samples will be collected before intranasal administration and 4 blood samples will be collected after oxytocin administration for all visits). Samples were kept chilled in ice and centrifuged within 1 h from collection at 1600 g for 15 min at 4 °C. Plasma was removed and initially frozen at -20 °C, then stored at -80 °C. Plasma samples and blood cells will be extracted and stored at -80 °C until the assays were performed. The centrifuging will be performed at

ACTSI and the samples will be stored at CRN until we are ready to transport some of the samples for the different laboratory to analyze it.

We intend to send some aliquots of plasma from each of these 8 samples to public health to quantify oxytocin concentration in the plasma and to quantify the exposome and metabolome (chemicals/pesticides).

Plasma will be analyzed for cytokines levels.

Blood cells from 4 blood samples (prior to OXT administration) will be sent to analyze the DNA methylation and/or to analyze OXTR polymorphism analysis.

The rest of blood cells and plasma will be kept safe at CRN unit for future analysis.

All these specimens are collected from healthy subjects and from patients with autism.

### **Randomization and blinding**

**Clinical trial for ASD subjects:** The trial will be a double-blind, placebo-controlled, several doses of oxytocin, within subject design study. Patients will undergo 4 clinical visits (in addition to a first pre-clinical visit) during which they receive 12 puffs (6 in each nostril) of 8IU total, 24IU and 48IU oxytocin (syntocinon) and placebo (assigned randomly). The placebo will contain the same ingredients as syntocinon, except the active molecule oxytocin. This is essential for making sure that the patient does not recognize the type of treatment he is receiving. Hence, both patients and the experimenter will be blind to the type of the treatment administered.

The pharmacy IDS of Emory will be in charge of the randomization sequence and one of the staff members of the team (who is not involved in testing procedures) will be de-blinded.

We will break the blind after testing 25 patients with ASD to check the results half-way for a mid-point analysis. The mid-point analysis will focus on measures where effect sizes are anticipated to be large enough that the risk of false positives is minimal. We are expecting larger effect size on some measures and therefore we break the blind for those measures to be analyzed and published. Additional data on these measures will continue to be collected and we will attempt to publish the combined analysis at the end to avoid publication bias.

However, the data collection will continue until a sample size equal to 50. Given that we are facing challenges with ASD recruitment and that the study requires the participation in 5 long visits, it is possible that the study will stop at N=30 or 40, in case the PI was not able to recruit more ASD. We also expect dropouts after recruitment. We believe that we will be able to test 30 patients with ASD.

It is possible that this project will be funded by other grant funds which will allow adding more participants (more 50 ASD). In this case, the PI will submit an amendment accordingly.

**Healthy subjects:** There will be only one clinical visit for healthy subjects and they will all receive placebo spray (12 puffs, 6 per nostril). The study will be conducted in a single-blind design. The PI is aware that the subject is receiving placebo. However, the participant will be told that he might

receive oxytocin or placebo. This is important in order to control for the placebo effect on behavior and brain activity.

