### **Statistical analysis:**

Power analysis (using G power 3.1 software) shows that a sample size of 50 subjects with ASD receiving 4 different treatments is needed to reliably detect (95% power) effect sizes small or larger (Cohen's  $d=0.2$ ) on one measure. In this study, we expect to find small to medium size effects of oxytocin inhalation on behavioral measures (based on previous meta-analysis of Bakermans-Kranenburg and Van I Jzendoorn. 2013). Authors found a combined effect size of  $d=0.32$  (95% confidence interval: 0.18-0.47). As mentioned above, we are planning to break the blind with  $N=25$  ASD subjects for a mid-way analysis, which is sufficient to detect effect sizes between medium and small (Cohen's  $d=0.3$ ). We expect larger effect sizes on measures of brain

activity (BOLD activity and functional connectivity). Therefore, these measures will be mainly analyzed during the mid-way analysis for potential publications. Of note, we are also planning to publish the combined analysis with the total number of subjects on the measures that were published mid-way to avoid any publication bias.

For healthy subjects, we need at least 30 subjects receiving on treatment to reliably detect (95% power) the differences between social and non-social conditions or emotional faces versus neutral faces in the aims above with an effect size between small and medium (Cohen's  $d=0.35$ ).

When comparing healthy subjects to patients with autism (placebo administration only), the above numbers are sufficient to reliably detect small effect sizes between groups (Cohen's  $d=0.2$ ) for one measure.

The PI will submit an annual report to the IRB and address whether the study is safe and whether it is appropriate to continue. This report will include compliance, review of eligibility, treatment review, summary of responses, survival, adverse events and safety monitoring rules.

Given that we do not expect serious adverse events and we are investigating the effects of this hormone on brain activity and behavior, we do not expect an early stopping.

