There will be analysis at various stages of the trial. We might need to analyze the behavioral and physiological data for data monitoring committee, in any or to write reports to NIH about the progress. There will be analysis of primary outcome measures of the different aims (cited above) during mid-way analysis (when we break the blind half way at  $N=25$  of ASD). The analysis will also be conducted at the final stage of the trial.

Brain imaging procedures using MRI, fMRI will be conducted at the Biomedical Imaging Technology Center (BITC) at Emory. Anatomical Image Acquisition: participants will be positioned supine in the MRI scanner (Siemens, Magnetom Prisma, Trio 3T) with instructions to lie motionless. Padded head restraint will minimize head movement during scanning sessions, each of which will begin with a 15 second scout scan to localize the position of the brain within the magnet. This will be followed by T1-weighted MPRAGE scan (TR= 2300 ms, TE = 4 ms, matrix = 256x256, FOV=256, slice thickness = 1.00 mm, gap = 0 mm).

**For aim 1, the primary outcome measure** consists of investigating the effects of different treatments (3 doses of oxytocin and one dose of placebo) on brain functional connectivity at rest in patients with ASD, using fMRI. During resting state functional image acquisition (8 minutes), participants will be asked to remain awake and not moving. Image acquisition will be obtained using a multi-band slice accelerated gradient echo-planar imaging (EPI) pulse sequence 179, 180 with the following parameters: TR = 1000 ms, TE = 24 ms, matrix = 74 x 74, FOV = 220 mm, slice thickness = 2.0 mm, 64 axial slices, to reduce magnetic susceptibility artifact in the OFC region.

The aim of this analysis is to determine whether there is target engagement for intranasal oxytocin by demonstrating differences between doses of IN-OT on BOLD rsFC or whether there is a simple oxytocin effect. We define target engagement OXT effect (TEE-OXT) as any differential effect between a dose of OXT from another dose of OXT on brain or behavior. We define oxytocin effect

(OXT-Effect) as any differential effect between oxytocin (any dose) and placebo administration in ASD.

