Initial preprocessing steps for single-subject resting-state fMRI data will be conducted with FSL software or SPM with the help and training of [name]. fMRI data will undergo standard preprocessing steps: realignment, slice-timing correction, volume registration, spatial normalization to MNI152 template, spatial smoothing with 5 mm FWHM Gaussian filter and temporal band-pass filtering (0.01-0.1 HZ). Corrections for head motion, whole-brain signals, ventricular signals, white matter signals. We will define specific regions of interest that includes the social brain network that we discussed in the sections above (MPFC, OFC, PCC, precuneus, insula, ACC, ventral striatum, amygdala, temporal areas, SMA etc). We will compare the functional connectivity between and within the different social brain networks (including the default, the salience network and temporal network) between the different treatment conditions. This analysis will be performed based on the GLM using corresponding regressors. We will also compute the rsFC between the different regions of interest by calculating a Pearson's correlation coefficient between the time series of the preprocessed functional MRI signals. In order to study target engagement effect on within network correlations, the resulting of the cross-correlation maps will be Fisher transformed to z-scores and fed into a 2-factor (4 treatment condition X 3 networks (default, salience, temporal); covariate: visit order) ANOVA. In order to study target engagement effect on between network correlations, the resulting of the cross-correlation maps will be Fisher transformed to z-scores and fed into a repeated Anova (4 treatment condition X 3 networks (Salience+Default; Salience+Temporal; Default+Temporal); covariate: visit order) ANOVA. In order to determine simple oxytocin effect, T-contrast maps will determine the differences in rsFC between placebo and each of the different doses of oxytocin. Multiple comparison correction will be conducted. The specificity of the results will also be conformed in a whole brain analysis. Given that baseline rs-FC is not acquired, and in order to account for non-specific fluctuations, we will use a two-stage GLM procedure during which we account for within-subject variability (across the different visits). Time regressor will be added to the model as a covariate to control for external factors that could influence rs-FC other than the treatment.

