Withdrawals, missing data and ineligible patients will be stated. Data will be controlled and double checked by the PI before publishing papers. Outliers will be investigated with statistical tools. Post-analysis will be checked for quality and checked for confounder factors, covariates. Additional precision on the type of analysis (behavioral, physiological and brain) will be submitted as amendments once the PI and staff members start working on the analysis of the data of the project.

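### The unblinded, publishable analysis at 25 ASD patients is justified by large anticipated effects, which do not control type I error, and neither it nor the final combined analysis has a stated alpha or confirmatory/exploratory status

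*Combined protocol and SAP*

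**What the plan says.** The Randomization and blinding section plans a mid-point analysis once 25 ASD patients have been tested. It gives this reason: "The mid-point analysis will focus on measures where effect sizes are anticipated to be large enough that the risk of false positives is minimal". It continues: "We are expecting larger effect size on some measures and therefore we break the blind for those measures to be analyzed and published". Collection then runs on towards 50 patients. The section allows for 30 or 40 if recruitment is hard, and says 30 is the number the team believes it can test.

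The Statistical analysis section says of the brain measures that "these measures will be mainly analyzed during the mid-way analysis for potential publications", and adds that "we are also planning to publish the combined analysis with the total number of subjects on the measures that were published mid-way". A later paragraph of that section describes the content of the look differently: "There will be analysis of primary outcome measures of the different aims (cited above) during mid-way analysis". On stopping, it says "we do not expect an early stopping".

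Two other statements might seem to bear on error control. Within the aim 1 resting-state analysis: "Multiple comparison correction will be conducted". At the end of the statistical text, after aim 5: "Additional precision on the type of analysis (behavioral, physiological and brain) will be submitted as amendments".

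The word exploratory is used only for the moderator and heterogeneity analyses and for the ASD-control comparisons. It is not applied to the mid-point analysis.

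**The concern.** The stated reason treats an expectation about effect size as protection against false positives. Type I error is the rejection rate when there is no effect, so it depends on the threshold and not on what was hoped for.

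The plan then gives each measure in the look two opportunities for a published claim, first at N=25 and again on data containing those 25 patients. It names no threshold for either and does not say which one counts. A reader of the N=25 paper would be told that the false-positive risk is minimal, with nothing in the plan to support that. The later paper is only a partial check, because it is not independent of the first.

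**Working it through.** **Inputs.** From the documents: first look at 25 ASD patients; final N of 50 (planned), or 30 or 40 (possible); four within-subject conditions. Not in the documents, so assumed: two-sided 0.05 at each look, with alternatives below. The main calculation uses a paired contrast between two conditions. Because most planned analyses are repeated-measures ANOVA, an F-test version is also given.

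**Step 1. The plan's nearest figure.** There is no stated alpha or overall error rate to reproduce. The closest figure is that N=25 suffices for Cohen's d=0.3; 95% power is taken from the companion N=50 statement. For a repeated-measures ANOVA with m=4 conditions, λ = f²·N·m/(1−ρ), with ρ assumed to be 0.5.
- 0.3 entered as Cohen's f: λ = 0.09×25×4/0.5 = 18, power 94.9%.
- 0.3 read as d, so f=0.15: λ = 0.0225×25×4/0.5 = 4.5, power 38%.
- Paired t-test with d as the standardised within-subject difference: noncentrality 0.3×√25 = 1.5, two-sided power 30%.

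Read as d, the ANOVA power rises to about 98% only if ρ is near 0.9. This matters for the charitable reading discussed under the objection. It has no bearing on type I error.

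**Step 2. One look.** With no effect, the simulated N=25 test rejected in 5.0% of trials. Anticipated effect size does not enter that calculation.

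**Step 3. Two looks.** The two test statistics have correlation √(25/N): 0.913, 0.791 and 0.707 for N = 30, 40 and 50. The chance of rejecting at either look is 0.05 + 0.05 − P(both).

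| Final N | Share of data at first look | Either look, normal approximation | Either look, paired t (simulated) | Either look, 4-condition F (simulated) | N=25 false positives still significant at the end |
|---|---|---|---|---|---|
| 30 | 25/30 = 83% | 6.9% | 7.0% | 7.1% | about 60% |
| 40 | 25/40 = 62.5% | 7.9% | 7.9% | 8.1% | about 41% |
| 50 | 25/50 = 50% | 8.3% | 8.4% | 8.5% | about 33% |

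Consistency check at N=30: P(both) is about 0.05×0.60 = 0.030, so 0.05 + 0.05 − 0.030 = 0.070. The final test taken alone rejects in 5.0% of null trials at every N.

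**Step 4. Other alphas.** At two-sided 0.01 per look, the either-look error is about 1.5% to 1.8%. At one-sided 0.05 it is about 6.7% to 8.0%. The excess over nominal persists in each case.

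**Step 5. Does other text close the gap?** The multiple-comparison sentence sits inside the aim 1 analysis and does not mention repeated looks. The promise of later precision means that a rule could be added by amendment, but the present plan has none.

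**The case against.** **No efficacy stop is planned, and a smaller N is tied to recruitment.** This stands. A reader might infer that the final analysis is itself inflated, or that the sample size will be chosen from unblinded results. The documents support neither. The combined test alone keeps its level, and the only reason given for stopping at 30 or 40 is difficulty in recruiting. Because N is left open after an unblinded look, a sentence confirming this is still worth having.

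**False-positive risk may mean the share of positive findings that are false.** High power does lower that share, but only if the anticipated effects are real. Step 1 shows that high power at N=25 for d=0.3 depends on how the effect size is read and on an unstated correlation. The plan expects brain effects to be larger, but gives no figure for them.

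**The combined publication is a safeguard.** It is partial disclosure and it addresses selective reporting. It does not control error, and at a final N of 30 it shares 83% of its patients with the first paper.

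**The increase is small.** Agreed: 2.0 to 3.4 percentage points per contrast. Testing many regions and contrasts matters more. Ten independent measures at a single look already give 1 − 0.95¹⁰ = 40%.

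**The descriptions of the look contradict one another.** This is a tempting reading but too strong. The primary outcomes of aims 1 to 3 are resting connectivity and BOLD activity, so brain measures and primary outcomes largely overlap. Plasma oxytocin is the clear exception. The fair criticism is that the measures are not listed.

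**A reader might infer that a group-sequential boundary is required.** It is not. No efficacy stop is planned, the Healthy subjects screening section says ASD testing is complete, and an exploratory label is sufficient.

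**Conclusion.** The concern holds. The false-positive rationale is wrong for type I error, and the plan gives no alpha and no status for either analysis. On the stated assumptions (two-sided 0.05 at each look, one contrast tested at both), the chance of at least one false claim is about 7% to 8.4%, against 5% for a single test. Between about a third and three fifths of N=25 false positives would survive into the combined paper, the larger share at the N of 30 that the team expects. The final analysis is sound on this point if it alone is confirmatory. The weakness lies in the claims made at N=25, it is modest per contrast, and it should be fixed.

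**What to change.** In the Randomization and blinding and Statistical analysis sections:
- Delete the sentence that links anticipated effect size to minimal false-positive risk.
- State one two-sided alpha.
- Make the final combined analysis the only confirmatory one, at full alpha.
- Label all N=25 results interim and exploratory, including in any paper.
- List the measures in the mid-point look, and say explicitly whether plasma oxytocin is among them.
- State the realised ASD sample size and that it was not set from unblinded results. The documents give 50, 30 or 40, and at least 30, and also say that ASD testing is complete.

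The cost is wording only. Final power is unchanged; the N=25 results can no longer be presented as confirmatory.

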**Storage:**

Saliva DNA samples will be stored in a locked place

Blood samples will be centrifuged into plasma and blood cells at the CRN unit and stored at -80°C at CRN unit until the PI is ready to transfer the tubes to laboratories for analysis. The PI will make sure that he has all the transfer material documents in place and all the procedures detailed in the IRB protocol before sending the samples for laboratories. All the samples that will be transferred to other locations for specific analysis will be de-identified and coded and will not have any personal identifiers related to participants' identity. Only the PI will have access to the identifiers and link between codes and participants' identity. Physical material such as files and folders (that includes identifiable information) will be stored in a secure and locked place. All the electronic excel data that are linked to identifiers will be saved on the psychiatry server (which is HIPAA compliant). Collaborators who will conduct the analysis cited above will collect the results in an excel sheet but will include only coded de-identified information. They will send the PI the excel files with the results via Emory email and only the PI will have access to the links between identifiers and the coded results.

Our collaborators at public health have communicated with us the details of the storage of the plasma samples for oxytocin measurement and metabolites/exposome/pesticides measurements:

Data files obtained from metabolic profiling will be stored on a secure, offsite RAID that was specifically designated for use by the Clinical Biomarkers Laboratory. Feature tables will be stored on the network hard drive available to Biomarkers personnel associated with the project only. All analyses of the result files will be logged, and include type of analysis, statistical parameters, date of analysis, investigator and summary of results. All method operational parameters will be printed and stored with raw analysis logs, and any alterations to instrumental configuration will be noted in a log book kept for that specific instrument. Laboratory notebooks will be maintained by all project personnel, with all entries made in ink. Due to the nature of the research completed by the Clinical Biomarkers Lab, all technical infrastructures required for data management are in place and can be adapted for use for this project.

